Aim 1: Investigate the efficacy of iCBT among Black and Latinx IBD patients with elevated psychological distress

We predict that compared to those who receive digital mood tracking, patients who are allocated to iCBT will have (a) lower psychological distress, as measured by the National Institutes of Health (NIH) Patient Reported Outcomes Measurement Information System (PROMIS) anxiety and depression scores and NIH Toolbox Perceived Stress Scale scores, (b) higher HRQoL on overall PROMIS-29 scores and (c) lower disease activity, as measured by patient-reported disease activity indices.

Aim 2: Evaluate implementation of iCBT among Black and Latinx IBD patients

We predict that (a) behavioral factors, such as elevated psychological distress, high self-efficacy, coping, and spirituality will be the strongest predictors of acceptance of iCBT and that other factors such as younger age, higher educational attainment, recent IBD diagnosis, and high disease activity will be associated with higher iCBT use and (b) modifiable individual and process level barriers and facilitators of iCBT use will be identified.

Participants will have IBD and elevated psychological distress and be recruited from the two outpatient clinical sites where the research physician and senior key personnel practice. The total estimated IBD population with clinical visits at Einstein/Montefiore is approximately 1,200 patients. In an average week, about 34 unique IBD patients receive care at one of the two study sites of which about 19% are Black and 30% are Latinx. About 85% have internet access, using active patient portal registration in the electronic medical record as a rough proxy. Based on estimates from the literature, the prevalence of anxiety or depression in IBD is around 20% and up to 66% with active disease.⁸ Thus, we estimate that on a weekly basis at least 6 and up to 22 Black or Latinx IBD patients attending a study site will have elevated anxiety or depression.

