various health insurance plans. The cost for individuals who do not qualify for health insurance coverage will come from the study budget. Participants will be instructed to export from the app a weekly data use report to the research physician's Montefiore email. The research physician will be linked to participant usage and progress through the app. There is an emergency resources section within the app that includes information on crisis help-lines and other resources for users in emergency situations. The app is available for use in iOS and Android systems as well as online through any web browser. App content is available in English with text translations in Spanish.

All participants will receive a unique link to complete a follow-up questionnaire at 48 weeks post intervention (Table 1). Non-responders will receive a reminder phone call twice weekly for 2 weeks and thereafter be considered lost to follow-up.

Table 1. Timeline and Sources of Data		
Baseline - REDCap Questionnaire (completed by patient at office visit or remotely)		
Socio-demographics	Assessment Tools	Clinical features

 ▪ Age ▪ Race/ethnicity ▪ Sex ▪ Birthplace ▪ Primary language ▪ Educational attainment ▪ Employment status ▪ Health insurance ▪ Marital status 	
 ▪ IBD disease activity index: Short Crohn's Disease Activity Index for Crohn's disease or Simple Clinical Colitis Activity Index for ulcerative colitis ▪ PROMIS-29 ▪ Perceived Stress Scale ▪ PROMIS Self-efficacy Managing Emotions ▪ PhenX Toolkit – Spirituality ▪ Brief Resilient Coping Scale 	
 ▪ IBD phenotype ▪ Disease duration ▪ IBD medications ▪ Previous/current psychiatric diagnosis, suicidal ideation or hospitalization
Follow-up at 84 weeks REDCap Questionnaire (completed by patient remotely)		
	Assessment Tools	
	
 ▪ IBD disease activity index: Short Crohn's Disease Activity Index for Crohn's disease or Simple Clinical Colitis Activity Index for ulcerative colitis ▪ PROMIS-29 ▪ Perceived Stress Scale ▪ PROMIS Self-efficacy Managing Emotions 	

3) Study Population

We aim to recruit 25 patients in each study arm for a total of 50 participants. Eligibility will be restricted to:

- age \geq 18 years
- race/ethnicity self-identified as Black/African American or Hispanic/Latinx
- established diagnosis of Crohn's disease or ulcerative colitis

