Other risks of the study are the risk of discomfort or distress answering questions about mental health and discomfort or distress addressing mental health through a digital platform. It will be made clear to participants that they may choose not to answer any questions they feel uncomfortable with and that use of the iCBT application is completely voluntary. Participants are also directed to seek immediate medical attention in case of any severe psychological distress e.g. suicidality. The research physician will have a password-protected provider interface to the iCBT platform that enables aggregate information regarding individual participant iCBT data usage.

7) Data Analysis

Aim 1: Investigate the efficacy of iCBT among Black and Latinx IBD patients with elevated psychological distress

The primary outcome will be the level of psychological distress (scores in the domains of anxiety and/or depression on the PROMIS-29 assessment tool) at 84 weeks between study arms. PROMIS-29 is a 29-item form that includes 4 questions in each of the domains of anxiety and depression.¹⁶ Higher scores indicate a greater level of the measured trait, and raw scores are converted to a T-score that centers at a mean of 50 with a standard deviation of 10 in the general population. The minimum clinically significant change in the domains of anxiety and depression has been shown to be 2.3-5.5 points.^{17,18} The other PROMIS-29 domains of physical function, fatigue, sleep disturbance, ability to participate in social roles, pain intensity and interference together give a measure of HRQoL.

Secondary outcomes will be the change in perceived stress, overall HRQoL and IBD disease activity. Perceived stress will be measured with the 10-item Perceived Stress Scale. Like PROMIS-29, higher scores indicate a higher level of the measured trait, and raw scores are converted to a T-score. The overall HRQoL will be measured with the PROMIS-29 including the non-anxiety/depression domains. Disease activity will be measured by the Short Crohn's Activity Index (for participants with Crohn's disease) or Mayo sub-scores (for participants with ulcerative colitis).

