Primary analysis will be by intention-to-treat with participants analyzed in the group to which they were randomized. We will use descriptive statistics to summarize socio-demographic and disease characteristics of both study groups and of app usage in the iCBT group: number of modules completed; weekly time spent on app; participation in community support groups. Our primary hypothesis is that participants in the iCBT group will have lower psychological distress scores compared to those in the digital mood tracking group post-intervention. To test the association between psychological distress (T-score for anxiety, depression) and study group, we will use Student's t-test if the normality assumption is met, or the Mann-Whitney U test if normality is appreciably violated. Assuming a minimum clinically significant change of a 5.5 points difference in T-scores between study groups with a standard deviation of \pm 6 points, a sample size of 40 participants (20 in each arm) will be needed to have 80% power at an alpha of 0.05. Targeting a recruitment sample size of 50 participants (25 in each arm) would allow for roughly 20% drop-out rate.

Our secondary hypotheses are that participants in the iCBT group will have lower perceived stress scores and higher HRQoL. To test these hypotheses, we will again use Student's t-test if the normality assumption is met or the Mann-Whitney U test if normality is appreciably violated. Finally, we hypothesize that elevated disease activity at baseline (Short Crohn's Disease Activity Index \geq 150 or Mayo sub-scores \geq 2) will be associated with achieving a minimum clinically significant change in T-score. To test the association between high baseline disease activity and minimum clinically significant change (as a dichotomous outcome), we will perform Chi-squared or Fisher's exact test.

Aim 2: Evaluate implementation of iCBT among Black and Latinx IBD patients

Participants randomized to iCBT will complete a survey as part of their follow-up assessment at 84 weeks to evaluate their acceptance of and satisfaction with iCBT.

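### For ulcerative colitis, Table 1 collects one disease-activity index and Section 7 analyses another; disease activity also has no stated between-arm test

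*Combined protocol and SAP*

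**What the plan says.** Section 2, Aim 1(c) predicts that the iCBT arm will have "lower disease activity, as measured by patient-reported disease activity indices".

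Table 1 in Section 2 lists what is collected and from where. Its baseline and follow-up blocks are both labelled as REDCap questionnaires, the follow-up one as "REDCap Questionnaire (completed by patient remotely". For colitis each block lists only the "Simple Clinical Colitis Activity Index for ulcerative colitis".

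Section 7, Aim 1 declares: "Secondary outcomes will be the change in perceived stress, overall HRQoL and IBD disease activity". It then says how the last of these is measured: "Disease activity will be measured by the Short Crohn's Activity Index (for participants with Crohn's disease) or Mayo sub-scores", with Mayo assigned to the colitis participants ("or Mayo sub-scores (for participants with ulcerative colitis"). The same section defines elevated baseline activity as a Short Crohn's Disease Activity Index of at least "150 or Mayo sub-scores" of at least 2, and tests it against reaching a minimum clinically significant change in T-score. Section 7, Aim 2 uses the same pair of cut-offs to split participants into high and low activity as a predictor of iCBT acceptance and app usage.

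On between-arm tests for the secondary outcomes, Section 7 states: "Our secondary hypotheses are that participants in the iCBT group will have lower perceived stress scores and higher HRQoL". The rule that follows (t-test, or Mann-Whitney if normality fails) is applied to those hypotheses.

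**The concern.** An analysis plan has to work on variables that the data schedule produces. Here the colitis variable in Section 7 is not in the schedule, and the colitis variable in the schedule is never mentioned in Section 7. Three uses depend on it: the colitis part of one secondary outcome, the Aim 1 baseline-activity hypothesis, and one of the Aim 2 predictors.

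If the gap stays open until the data are in, someone has to choose an index or a cut-off at that point. A high/low split chosen with the outcomes in view is no longer pre-specified, and a reader could not tell whether it was.

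The second matter is smaller. Aim 1(c) is a prediction about the treatment effect on disease activity, yet no comparison of arms is written for it. Nor does the plan say how two indices on different scales, one per disease, would enter such a comparison.

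**Working it through.** **1. The colitis measure, place by place**

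| Place | Colitis measure | Use |
|---|---|---|
| Section 2, Aim 1(c) | patient-reported indices, not named | between-arm prediction |
| Section 2, Table 1, baseline | Simple Clinical Colitis Activity Index | collected by REDCap questionnaire |
| Section 2, Table 1, follow-up | Simple Clinical Colitis Activity Index | collected by REDCap questionnaire |
| Section 7, Aim 1, secondary outcomes | Mayo sub-scores | measures the outcome |
| Section 7, Aim 1, baseline-activity hypothesis | Mayo sub-scores, high at 2 or more | predictor of T-score response |
| Section 7, Aim 2 | Mayo sub-scores, 2 or more against below 2 | predictor of acceptance and usage |

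Table 1 names the Simple Clinical Colitis Activity Index twice and Mayo never. Section 7 names Mayo four times (twice under Aim 1, twice under Aim 2) and the Table 1 index never.

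**2. Can the text settle it?** There are two readings, and each leaves a gap.

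- If Table 1 is right, colitis participants have a score on an index for which Section 7 gives no cut-off and no conversion to Mayo.
- If Section 7 is right, Table 1 is wrong. The Mayo sub-scores are still not named, and the plan does not say whether 2 applies to each sub-score or to a sum.

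**3. Crohn's disease as a comparison.** The Short Crohn's Disease Activity Index appears in Table 1 and throughout Section 7, with a cut-off of 150 on its own scale. One sentence in Section 7 shortens its name. There is no conflict.

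**4. Between-arm tests.** Three secondary outcomes are declared: perceived stress, HRQoL and disease activity. The t-test/Mann-Whitney rule covers the first two. The only Aim 1 test involving disease activity (Chi-squared or Fisher) relates baseline activity to T-score response, which is a different question from treatment arm against change in activity. So 2 of 3 have a stated comparison.

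**5. The plan's own sample size.** Inputs from Section 7: difference 5.5, SD 6, alpha 0.05 (taken as two-sided), power 80%. The normal approximation is n per arm = 2 × (1.96 + 0.84)² × (6/5.5)² = 18.7, so 19. The t-test solution is 19.7, so 20 per arm, with power 0.806. Inflation for drop-out: 40/(1 − 0.20) = 50. The figure reproduces. It rests only on the PROMIS T-score, so the conflict does not touch it. No effect size or SD is given for any activity index, so power for Aim 1(c) cannot be computed.

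**6. Precision of a disease-activity comparison.** The 95% half-width in SD units is t(0.975, 2n − 2) × √(2/n).

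- All completers on a common standardised scale, n = 20 per arm: 2.024 × 0.316 = 0.64 SD.
- One disease alone, with an assumed colitis share of 30–70% (not in the documents), so n = 6 to 14 per arm: 1.29 to 0.78 SD.

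**The case against.** The strongest reply is that Table 1 already answers the question. Its headings say what is in the questionnaire, Aim 1(c) asks for patient-reported indices, and the mention of Mayo could be a drafting slip that the live questionnaire would resolve at once. Part of this stands: it would be wrong to say that the documents are silent on the questionnaire's content. But Section 7 also states what activity will be measured by, and nothing marks either text as superseded. Even if Table 1 is accepted, the high/low rule still has no cut-off on the collected index.

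A reader might also infer a large numerical loss. With a colitis share of 30–70%, 12 to 28 of 40 completers (0.30 × 40 to 0.70 × 40) would be unclassified in the Aim 1 baseline-activity test. The half-width for a difference in proportions, 1.96 × √(2 × 0.25/(N/2)), would go from 31 points at N = 40 to 37 at N = 28 or 57 at N = 12. The documents do not support this as a finding. It needs an assumed colitis share, an even high/low split, 50% response, and a team that discards every colitis participant instead of setting a cut-off. The test is weak at 31 points even with no loss.

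Nor can one say that the Aim 2 tests could not reach significance. With 6 classified participants the smallest two-sided Fisher p is 1/15 = 0.067, but that count is 30% of 20 iCBT completers and fits acceptance only, which needs the follow-up survey. App usage comes from the app, so up to 25 iCBT participants can contribute. At the same share 0.30 × 25 = 7.5, so 7 or 8 are classified, and with 7 the smallest p is 1/35 = 0.029. Usage is also to be analysed as continuous, where this limit does not apply.

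Finally, analysis by disease type is not the only sound way to handle two scales. The plan needs to state a method, not that particular one.

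**Conclusion.** The contradiction is real and can be read from the text without any calculation. It is an error as written, not merely missing detail: the classification rule in Section 7 cannot be applied to the colitis data that Table 1 schedules. It reaches the colitis part of one of three secondary outcomes, one Aim 1 hypothesis and one Aim 2 predictor. How many participants that means cannot be computed from the documents.

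The missing between-arm test for Aim 1(c) is also real but secondary, since the existing rule could be extended in one clause.

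This should be fixed before analysis, but it does not threaten the trial's main result. The conclusion rests on the current text alone; the live questionnaire may show that only one of the two passages needs correcting.

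**What to change.** - Check which colitis index the live REDCap questionnaire contains, and reconcile Table 1 and every Section 7 mention (Aims 1 and 2) to that one index.
- State the analysis cut-off for high activity on that index's own scale, with its justification and a date before the data are analysed.
- If the index is Mayo, correct Table 1, name the patient-reported sub-scores, and say whether the cut-off applies to each or to a sum.
- In Section 7, extend the existing between-arm rule to change in disease activity in a way that respects the two scales: by disease type, or by a disease-stratified or standardised comparison. Report the estimate with its confidence interval. Alternatively, label the outcome descriptive.

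The cost is a check of the questionnaire and a few sentences. No new assessment is needed if either index is already collected. The real work is justifying a cut-off if the Table 1 index is the one in use. The downside is imprecision: at about 20 completers per arm the interval will be wide under any of these options, and wider still by disease type, so a null result should not be read as evidence of no effect on disease activity.

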All consenting participants will complete a baseline questionnaire. Eligible participants will undergo 1:1 randomization using computer-generated variable 2 and 4 block allocation to either the iCBT or the digital mood tracking study arm. Allocation sequence will be concealed from the study team using opaque sealed envelopes. At the time of participant consent, the research physician will select the next consecutive envelope that will determine participant group assignment to either iCBT or digital mood tracking. All participants will receive a one-page brochure on mental health recommendations from the National Institute of Mental Health. Participants initially randomized to the digital mood tracking app will be offered 84 weeks of iCBT after completing the post-intervention study assessment/interview.

The digital mood tracking application (app) selected for this study (Pixel™) allows participants to log their mood each day by way of a facial expression emoji and a free-text box. This app is commercially available free of charge through iOS and Android app stores with English and Spanish language options.

The iCBT platform selected for use in this study (Sanvello™) is an evidence-based mobile app created by clinical experts that has been shown to decrease depression, anxiety, and stress and to increase self-efficacy in a non-IBD population.¹⁵ App features include: daily mood tracking; guided journeys (e.g. psychoeducational content providing background information about cognitive behavioral therapy and instructing users on how to use app tools to maintain motivation and interest); coping tools (e.g. meditation, goal setting, and negative thought redirecting activities); weekly progress assessments; community support board. Study participants will receive a 2-month subscription for the app. Subscription is covered by

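### The primary analysis is labelled intention-to-treat but has no rule for missing follow-up scores and ignores the baseline score, so non-random loss of about 20% could bias it in either direction

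*Combined protocol and SAP*

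**What the plan says.** Section 7, Aim 1, defines the analysis set in one sentence: "Primary analysis will be by intention-to-treat with participants analyzed in the group to which they were randomized". The endpoint is a follow-up level: "The primary outcome will be the level of psychological distress" on the PROMIS-29 anxiety and/or depression scales. For the comparison, "we will use Student's t-test if the normality assumption is met, or the Mann-Whitney U test if normality is appreciably violated". No covariate is named.

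The sample size is built on "a 5.5 points difference in T-scores between study groups" and an SD of 6. This gives 40 participants, raised to 50 because that "would allow for roughly 20% drop-out rate".

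Section 2 (Study Design) gives non-responders two weeks of reminder calls, after which they will "thereafter be considered lost to follow-up". Nothing in the document says what the analysis then does with them: there is no imputation, model-based method or sensitivity analysis. Table 1 shows that the PROMIS-29 is collected at baseline as well as at follow-up.

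Four provisions bear on who completes follow-up:
- Controls "will be offered 84 weeks of iCBT after completing the post-intervention study assessment/interview" (Section 2).
- Participants in either arm can receive a $20 gift card for the end-of-study questionnaire (Section 5).
- iCBT participants are asked to export a weekly usage report (Section 2).
- iCBT participants also have an acceptance and satisfaction survey at follow-up (Section 7, Aim 2).

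**The concern.** An intention-to-treat label leads a reader to expect an answer about all 50 randomised participants. Followed as written, the plan gives an answer about those with a follow-up score, planned at about 40. For the unadjusted difference to be unbiased, the effects of loss must cancel between the arms, for example because loss is unrelated to distress or because its mechanism and rate are the same in both.

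There are reasons to doubt that here. The arms differ in what follow-up offers and in what it demands. Aim 2 itself predicts that distress and disease activity relate to acceptance or use of iCBT. If engagement also affects return of the questionnaire, loss in the iCBT arm would not be random. At stake are the primary estimate and the error rate of its test. The planned test also discards a baseline score that could protect against part of the problem.

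**Working it through.** **1. The plan's own figure.** Inputs from Section 7: difference 5.5, SD 6, alpha 0.05 (taken as two-sided), power 80%.
- Normal approximation: n per arm = 2 × (1.96 + 0.84)² × 6² / 5.5² ≈ 18.7, so 19. The exact t-test gives 78.5% power at 19 per arm and 80.6% at 20. The stated 20 per arm is correct.
- Drop-out: 40 / (1 − 0.20) = 50, as stated. The power calculation counts 40 of the 50, which fits an analysis of observed scores.
- Scale: SE at 20 per arm = 6 × √(2/20) = 1.90. The smallest significant difference is 3.84 points.

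**2. How loss becomes bias.** Let p be the share lost in an arm, and g the mean score of those lost minus the mean of those observed (positive = more distressed). The observed-case difference then favours iCBT by

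bias = p(iCBT) × g(iCBT) − p(control) × g(control).

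The documents give no value for p by arm or for g. The values below are assumptions that keep total loss at 10 of 50, with no true effect.

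| Loss iCBT / control | g iCBT / control | Bias (points) | Two-sided rejection rate |
|---|---|---|---|
| 20% / 20% | 6 / 6 | 0 | 5% |
| 32% / 8% | 0 / 0 | 0 | 5% |
| 32% / 8% | 3 / 3 | 0.96 − 0.24 = 0.72 | 6.5% |
| 32% / 8% | 6 / 6 | 1.92 − 0.48 = 1.44 | 11% |
| 32% / 8% | 6 / −6 | 1.92 + 0.48 = 2.40 | 23% |
| 8% / 32% | 6 / 6 | 0.48 − 1.92 = −1.44 | as for +1.44, but against iCBT |

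Unequal loss alone gives no bias, and reversing the pattern reverses the sign.

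**3. What the baseline score recovers.** Simulation assumptions: 25 per arm, SD 6, no true effect, loss 30% in iCBT and 10% in control.
- *Higher baseline distress raises loss* (logistic slope 0.5 to 1.5 per SD, baseline to follow-up correlation 0.3 to 0.7). The unadjusted comparison has bias of about 0.2 to 1.4 points and type I error of about 5% to 10%. The baseline-adjusted comparison has bias of about 0 and type I error of about 5%.
- *The follow-up score itself drives loss* (slope 1.5, iCBT arm only). Bias is about 2 points unadjusted. It is still about 1.0 to 1.5 points after adjustment at correlations of 0.5 to 0.7.

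**4. Effect of adjustment on power.** The residual SD is 6 × √(1 − r²). At 20 per arm, ignoring the one degree of freedom spent on the covariate:
- r = 0.3: SD 5.72, power 84%
- r = 0.5: SD 5.20, power 90%
- r = 0.7: SD 4.28, power 98%
- unadjusted: SD 6, power 80.6%

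**The case against.** The strongest reply is that the plan is silent, not wrong. It nowhere specifies a complete-case analysis, and the direction and size of any bias are assumed. Much of this stands, and it rules out several stronger readings.

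- *A reader might infer that the design rewards follow-up only in controls.* It does not. The gift card and the reminder calls apply to both arms. What is control-only is an additional incentive, the later offer of iCBT. Even that wording may describe timing rather than a condition, and Section 2 says the subscription is covered by various health insurance plans.
- *A reader might infer that the bias favours iCBT.* The documents give neither loss by arm nor any link between distress and loss. The opposite pattern is equally open.
- *A reader might infer a badly inflated error rate.* Type I error of 8% to 12% under baseline-dependent loss needs a steep slope, about 1.5 per SD, acting in the iCBT arm only. With the same slope (1 or 2) in both arms, 30%/10% loss and correlation 0.5, bias is 0.55 to 0.69 points and type I error about 5.5%.
- *A reader might infer that multiple imputation is needed.* In a 1,000-run check under baseline-dependent loss, imputation by arm with six predictors removed no more bias than ANCOVA on observed cases. It raised the SD of the estimate from 1.69 to 1.95 and gave a conservative type I error of 2.2%.

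What does not stand is the suggestion that silence is harmless. That only observed cases enter is an inference, but neither named test can use a participant without a follow-up score, and the 40-of-50 arithmetic fits no other reading.

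**Conclusion.** The point holds in a limited form. The intention-to-treat label settles the arm in which a participant is counted. It does not settle what happens to the roughly 10 of 50 without a follow-up score, and the primary test leaves the baseline score unused. Unequal, non-random loss is plausible, but its direction is unknown.

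Under the baseline-dependent assumptions in step 3, the upper bias of 1.4 points is about a quarter of the 5.5-point design difference (1.4 / 5.5 = 25%) and below the 2.3-point lower end of the stated minimum important change. Bias is nil if mechanism and rate are the same in both arms. Outcome-dependent loss can do more harm, and baseline adjustment only partly removes it. All loss rates, slopes and correlations are assumptions. The sample size itself is correct. The change is worth making mainly because adjustment costs almost nothing, protects against one form of bias and adds power.

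**What to change.** In Section 7, Aim 1:

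1. Replace the unadjusted test with an ANCOVA of each primary follow-up T-score on arm and the same domain's baseline T-score. The normality check then applies to the residuals.
2. State that this analysis uses randomised participants with an observed follow-up score, in their randomised arm. Do not present it as a full intention-to-treat analysis of all 50.
3. Report the number lost, with reasons where known, by arm.
4. Add one sensitivity analysis covering all 50: take missing scores as predicted from arm and baseline, then shift them by 2.3 and 5.5 points, in either arm. The arm mean moves by the share lost times the shift. At 20% loss this is 0.20 × 2.3 = 0.46 or 0.20 × 5.5 = 1.10 points, so a reader can see whether the conclusion survives.
5. Multiple imputation by arm is optional.

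The 20% allowance also depends on the length of follow-up, which the document gives as 48 weeks in some places and 84 in others. Those statements must be reconciled.

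The cost is revised wording and a little more analysis work. No new data, visits or participants are needed.

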- elevated psychological distress: at least one T-score within two standard deviations above the mean in the domains of anxiety or depression on the National Institutes of Health Patient Reported Outcomes Measurement Information System-29 (PROMIS-29) with or without a T-score within two standard deviations above the mean for perceived stress on the National Institute of Health Toolbox Perceived Stress Scale (Perceived Stress Scale)
- internet access (smartphone/mobile device with data plan, computer with internet)
- ability to provide informed consent in English or Spanish

Exclusion criteria are:

- PROMIS-29 anxiety or depression T-scores in the severe range (above 2 standard deviations)
- Current suicidal ideation, past suicidal attempt or hospitalization

4) Participant Recruitment

Recruitment will be active and occur during in-person study site visits. If in-person visits are not possible (e.g. ongoing public health crisis), recruitment will occur via telemedicine visits. All IBD patients will be invited to participate. We anticipate enrolling 1-2 participants weekly into the trial.

For patients recruited during an in-person visit, the research physician/assistant will approach patients during their visit who meet the screening questions (based on age, race/ethnicity, diagnosis of IBD, internet access) to confirm eligibility. After the informed consent process, patients will complete a study questionnaire via a REDCap survey on a study site computer. Responses to this initial questionnaire will determine eligibility for randomization into the study based on the inclusion/exclusion criteria. Upon completion of the questionnaire, computer-automated scores will be generated. Patients with severe psychiatric distress or suicidality will be linked to psychiatric services at Montefiore. The research physician/assistant will inform patients of their eligibility to be randomized into the trial.

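### The primary test leaves out the baseline PROMIS score that decides eligibility, and it moves to Mann-Whitney on an undefined look at normality

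*Combined protocol and SAP*

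**What the plan says.** Section 7 (Data Analysis, Aim 1) states: "The primary outcome will be the level of psychological distress", meaning the PROMIS-29 anxiety and/or depression scores at follow-up, compared between arms. The test is Student's t-test "if the normality assumption is met, or the Mann-Whitney U test if normality is appreciably violated". No covariate, regression or change score is attached to this comparison. No normality test, cut-off or timing governs the choice between the two tests.

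The sample-size statement in the same section reads "Assuming a minimum clinically significant change of a 5.5 points difference in T-scores between study groups". It adds an SD of 6, 20 analysed per arm, 80% power and alpha 0.05, with 50 recruited to allow for about 20% drop-out.

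On baseline, Section 2 has every consenting participant fill in the baseline questionnaire, and Table 1 lists PROMIS-29 in it. Section 4 says: "Responses to this initial questionnaire will determine eligibility for randomization into the study based on the inclusion/exclusion criteria". Under Section 3, a participant needs an elevated T-score in at least one of the two domains and is excluded if either is more than 2 SD above the mean.

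The same pair of tests is planned for perceived stress and HRQoL. For these, Section 7 first says "Secondary outcomes will be the change in perceived stress, overall HRQoL and IBD disease activity", but the hypothesis tested is that "participants in the iCBT group will have lower perceived stress scores and higher HRQoL".

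**The concern.** A baseline measure of the outcome is usually the strongest available predictor of its follow-up value. Here it is collected before randomization because the entry criteria depend on it, and the primary test then ignores it. In a trial with 40 analysed patients, that gives up precision that costs nothing to recover. Randomization is in blocks of 2 and 4 with no stratification described, so nothing else in the design deals with chance baseline differences.

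The switch is a separate weakness. The design rests on a mean difference of 5.5 points, but Mann-Whitney compares ranks and does not estimate that difference. Which quantity the trial reports would be settled after looking at the outcome data, by a criterion that nobody has written down.

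For the secondary outcomes, the move between change and scores leaves it unclear whether baseline enters at all.

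**Working it through.** **Inputs from Section 7:** difference 5.5 points, SD 6, 20 analysed per arm, alpha 0.05 (taken as two-sided, which reproduces the stated N), power 80%, 50 recruited.

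**Input not in the documents:** r, the correlation between baseline and follow-up T-scores among enrolled patients. It is varied below.

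**1. The plan's own figure.** Noncentrality = 5.5 / (6 × √(2/20)) = 5.5 / 1.897 = 2.899. With 38 df the critical value is 2.024 and power is 80.6%. Twenty per arm is the smallest n that reaches 80%, and 40 / (1 − 0.20) = 50. The plan's sample size is right for the test it names.

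**2. Adding baseline.** The residual SD becomes SD × √((1 − r²)(1 + 1/36)), with 37 df. The factor 1 + 1/36 is the average price of estimating the baseline slope with 40 patients. The CI half-width is the critical t × residual SD × √(2/20).

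| Analysis at SD 6, 20 per arm | Residual SD | Power | 95% CI half-width |
|---|---|---|---|
| Unadjusted | 6.00 | 80.6% | 3.84 |
| Adjusted, r = 0 | 6.08 | 79.5% | 3.90 |
| Adjusted, r = 0.3 | 5.80 | 83.1% | 3.72 |
| Adjusted, r = 0.4 | 5.57 | 85.9% | 3.57 |
| Adjusted, r = 0.5 | 5.27 | 89.5% | 3.38 |

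Simulation of 40,000 adjusted analyses per setting gave 79.5%, 83.2%, 85.9% and 89.7%. The two approaches break even at r = 0.17.

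**3. A simple change score is not a substitute.** If baseline and follow-up SDs are both 6, the SD of change is 6 × √(2(1 − r)). At r = 0.3 this is 7.10 and power falls to 66.6%. Only at r = 0.5 does it match the unadjusted test (80.6%).

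**4. Effect of the entry rule (assumed scenario, not trial data).** Take a population SD of 10, mean 50 to 55, between-domain correlation 0.6 to 0.8 and baseline-to-follow-up correlation 0.5 to 0.8. Keep those whose higher domain score is above 50 and at most 70. Among those kept, r is 0.34 to 0.69 and the follow-up SD is 7.8 to 9.4. Power is then 44–58% unadjusted and 49–80% adjusted. The gain is about 3.5 to 5 points at population correlation 0.5 and 21 to 26 points at 0.8.

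**5. The switch.** The plan gives no rule, so a Shapiro-Wilk test at 0.05 in each arm was assumed. In 20,000 null simulations at 20 per arm, type I error was 5.3% with normal data (switching in 9.8% of runs) and 5.4% with skewed data (switching in 78%). If the open criterion were used to pick the smaller p-value, it would be 6.1% to 6.3%. The main harm is therefore the change in what is estimated, not inflation of error.

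**6. Sensitivity of the planned t-test to the SD.** Power is 81% at SD 6, 68% at 7, 56% at 8 and 40% at 10. The n per arm for 80% power is 20, 27, 35 and 53. This bears on the sample size and does not itself argue for adjustment. It matters because the plan gives no source for SD 6 and does not say whether it is the SD of level or of change.

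**The case against.** The planned analysis contains no error: an unadjusted t-test, powered as an unadjusted t-test, is coherent and unbiased under randomization. That stands, and it limits the point to efficiency and clarity. At r = 0.3 the interval narrows by only about 3% (3.84 to 3.72).

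The gain depends on an r that the documents do not give, and the follow-up interval is itself stated as both 48 and 84 weeks. This also stands. The large gains in the entry-rule scenario largely restate the assumed correlation of 0.8 and should not carry the argument. But the downside is bounded at about one point of power.

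A third objection is that baseline may be incomplete: inclusion needs only one elevated domain, and Section 6 tells participants that "they may choose not to answer any questions they feel uncomfortable with". Section 2 also opens the allocation envelope at consent, whereas Section 4 places the questionnaire after consent. However, the exclusion applies to either domain, so taken literally it cannot be checked without both scores. What remains is that a missing-baseline rule is prudent for the primary domains too.

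Finally, Mann-Whitney can be accompanied by a Hodges-Lehmann shift with a CI in T-score points. That is true, but the plan does not name it, and it is still a different quantity from the mean difference used in the sample-size calculation.

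**Conclusion.** The concern holds as a recommended improvement. The primary comparison is valid and correctly sized for its stated assumptions, but it ignores a covariate that the entry rules require. At SD 6 and 20 per arm, adjustment moves power from 80.6% to 83–90% for r between 0.3 and 0.5, and to 79.5% if r is zero. These figures rest on the assumed r and on the plan's SD of 6. If the SD is nearer to that in the entry-rule scenario, adjustment alone reaches about 80% only at the top of the assumed correlation range, so it does not rescue a sample size built on too small an SD. The normality switch does little to type I error if a rule is followed, but it leaves the estimated quantity undecided until the data are seen.

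**What to change.** For each of anxiety and depression, make the primary analysis a linear model of the follow-up T-score on arm and that domain's baseline T-score. Report the adjusted mean difference with its 95% CI, read against 5.5 points. Remove the normality-triggered choice and keep Mann-Whitney as a sensitivity analysis.

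Use the same model for perceived stress and HRQoL. With baseline in the model, the arm difference is identical whether the outcome is written as level or as change, because subtracting baseline shifts only the baseline coefficient, by one. That settles the inconsistent wording. HRQoL first needs one defined score, or one model per domain. Disease activity stands in the same secondary-outcome sentence, but Section 7 names no between-arm test for it, so it needs its own decision.

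In the power statement, give the source and type of SD 6 and show power at SD 7, 8 and 10.

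The cost is wording only, with no extra patients, visits or items. One degree of freedom is spent, worth about one point of power at SD 6 if baseline turns out to be uncorrelated. Because items may be skipped, add a short rule for a missing baseline value. It is needed mainly for perceived stress and HRQoL, and is worth stating for the primary domains as well.
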